2.3 Exploratory objectives

These are to be performed at Hackensack Meridian Health Center for Discovery and Innovation

- Plasma product analysis for cytokines, mannose-binding lectin (MBL), procalcitonin (PCT), C-reactive protein (CRP), Human neutrophil lipocalin (HNL), Annexin V, Surfactant protein D (SP-D), as well as microRNAs. It may not be feasible to draw samples on every plasma bag.
- Patients' cytokines and chemokines levels prior to treatment, +2 and +4 weeks (+/- 3 days) post randomization.
- Patient's gut microbiota diversity and composition prior to treatment, +3 day, +7 day, +2 weeks, +4 weeks, and +2 months post randomization.

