 - 5. Myalgias
 - 6. Headaches
 - 7. Other symptoms that the patient attributes to their COVID-19 infection

- New medical conditions, AE evaluation
- Safety assessment
- Rectal swab for microbiome at day +3 and day +7 to be sent to the CDI if possible.

5.2.4 Post enrollment: 2 weeks (+/- 3 days), 4 weeks and 2 months (+/- 5 days). Preferably in person.

- COVID-19 symptom screen (Y/N)
 1. Fever (T max)
 2. Cough
 3. Shortness of breath
 4. Ageusia and/or anosmia
 5. Myalgias
 6. Headaches
 7. Other symptoms that the patient attributes to their COVID-19 infection
- New medical conditions, AE evaluation
- Safety assessment
- Serological testing: anti-SARS CoV-2 titers if possible.
- Swab for COVID-19 testing at 2 weeks, and again at 4 weeks if week 2 is positive.
- Exploratory blood test for cytokines/chemokines at +2 and +4 weeks to be sent to the CDI if possible.
- Rectal swab for microbiome at +2 weeks, +4 weeks, and +2 months to be sent to the CDI if possible.

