8.1 Hypothesis

The primary objective is the hospitalization rate of patients with early COVID-19 infection at high-risk of admission. Suppose the hospitalization rate by 21 days from therapy initiation is 8% for the Treatment group (P_t) and 18% for the Control group (P_c). This phase II design will aim at the following hypothesis:

The design has a type I error rate at 0.05 with statistical power at least 0.80.

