8.3.4 Exploratory

- Descriptive statistics will be used to characterize the patients' cytokines, chemokines, plasma products (mannose-binding lectin (MBL), procalcitonin (PCT), C-reactive protein (CRP), human neutrophil lipocalin (HNL), annexin V, surfactant protein D (SP-D), microRNAs) and gut microbiome at pre-infusion treatment day, + 3 and +7 days (gut microbiome), +2 and +4 weeks (+/- 3 days) and +2 months (gut microbiome) post randomization. Frequency and percentages for categorical variables and mean (SD) or median [IQR] for the continuous variables based on the normalization of the data.

Univariate test will be performed in terms of identifying the association between exploratory objective and the hospitalization rate, Mantel-Haenszel test for categorical variables, and t-test or its non-parametric version for the continuous variables based on the normalized of the data. Analysis of the exploratory objectives will primarily be descriptive.

P-value less than 0.05 will be considered significant. All statistical analyses will be performed using RStudio (Version 0.99.902) and SAS (Version 9.4).

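### Exploratory marker tests in section 8.3.4 ignore randomized arm, so for markers sampled after randomization in both arms a treatment shift may mimic or mask a link with hospitalization

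*Combined protocol and SAP*

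**What the plan says.** Section 8.3.4 describes the exploratory markers and then adds a testing step: "Univariate test will be performed in terms of identifying the association between exploratory objective and the hospitalization rate". The tests are "Mantel-Haenszel test for categorical variables, and t-test or its non-parametric version for the continuous variables". The section ends with the rule "P-value less than 0.05 will be considered significant". It names no arm term, no arm stratum and no within-arm analysis. It also says that "Analysis of the exploratory objectives will primarily be descriptive".

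Two groups of patient markers are collected after randomization without restriction to one arm:
- Section 2.3 lists "Patients' cytokines and chemokines levels prior to treatment, +2 and +4 weeks (+/- 3 days) post randomization".
- Section 5.2.3 lists "Rectal swab for microbiome at day +3 and day +7 to be sent to the CDI if possible". Section 5.2.4 continues the swabs to 2 months and repeats that exploratory samples are sent if possible.

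In the text available, pre-treatment samples appear only under the infusion day (5.2.2), and plasma-product measures exist only for plasma that is given. Sections 4.1, 5.2.2 and 5.2.5 allow plasma for Control patients once they are admitted.

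The design rests on an arm difference in the same outcome: "Suppose the hospitalization rate by 21 days from therapy initiation is 8% for the Treatment group", against 18% for Control (8.1).

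**The concern.** If treatment changes both a marker and the admission rate, a test that pools the arms picks up a marker-admission association made of those two effects, even when the marker says nothing about admission within either arm. If treatment moves the marker against the direction of a real link, the two partly cancel and the link is missed. Both effects grow with the treatment effect on admission, so they are largest when plasma works.

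An arm shift in a marker is plausible on the protocol's own account. Section 1.1 offers modification of the inflammatory response as a possible mechanism, and section 5.2.2 gives hydrocortisone premedication with the infusion. At stake is an exploratory report that names a marker as related to hospitalization when it only repeats the arm comparison, or that drops a marker worth following.

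**Working it through.** **Inputs from the documents.** Admission rates 8% and 18% (8.1); 153 per arm at full enrolment (8.2); threshold 0.05 (8.3.4).

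**Assumptions.** Two-sided tests, since 8.3.4 does not state sidedness; a normal marker with SD 1 within arm; a treatment shift of *d* SD, for which the documents give no value; complete sampling; and, for steps 1 to 3, no Control plasma before the sample.

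**The plan's own figure.** A fixed one-sided 0.05 test of 18% against 8% with power 0.80 needs 139 per arm. Simulating the section 8.2 boundaries at 51, 102 and 153 per arm gives type I error 0.050 and power 0.80 to 0.81. The 306 patients therefore reproduce. The plan states no power for the marker tests.

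**Step 1: arm mix by admission status.**
- Admitted: 153 × 0.08 = 12.24 and 153 × 0.18 = 27.54, total 39.78. Treatment share 12.24/39.78 = 0.308.
- Not admitted: 140.76 + 125.46 = 266.22. Treatment share 140.76/266.22 = 0.529.
- Difference in shares: 0.221.

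**Step 2: false link.** With no within-arm link, the pooled difference (admitted minus not admitted) is −0.221*d*. Mixing the arms raises the within-group variance to about 1 + 0.245*d*², so SE = √[(1 + 0.245*d*²)(1/39.78 + 1/266.22)].
- *d* = 0.5: 0.1105/0.175 = 0.63, rejection Φ(0.63 − 1.96) + Φ(−0.63 − 1.96) ≈ 0.097.
- *d* = 1: 0.221/0.190 = 1.17, rejection ≈ 0.21.

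Simulation agrees: about 6% to 7% at 0.25 SD, 8% to 10% at 0.5 SD, 20% to 21% at 1 SD and 34% to 36% at 1.5 SD, against about 5% with an arm term. With half the samples, the pooled figures are about 6% to 8% at 0.5 SD and 13% at 1 SD. For a binary marker with Treatment/Control prevalence 65%/35%, the single-stratum Mantel-Haenszel test rejects in 12% of trials and the arm-stratified test in 5%. With equal admission rates (18% in both arms) and *d* = 1, the pooled test returns to about 5%, which confirms the cause.

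**Step 3: masked link.** Take a true within-arm difference of +0.5 SD in admitted patients, with treatment raising the marker by *d*.
- Arm-adjusted: information 12.24 × 140.76/153 + 27.54 × 125.46/153 = 11.26 + 22.58 = 33.84, SE = 1/√33.84 = 0.172, z = 2.91, power Φ(0.95) ≈ 0.83 (simulated about 0.82).
- Pooled, *d* = 0.5: (0.5 − 0.1105)/0.175 = 2.22, power about 0.60.
- Pooled, *d* = 1: (0.5 − 0.221)/0.190 = 1.47, power about 0.31.

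**Step 4: where an arm term fails.** Suppose a share *x* of admitted Control patients have had plasma before the sample, and plasma shifts the marker by *d*. Admitted and non-admitted Control patients then differ by *xd* with no true link. The arm-adjusted estimate is about (22.58/33.84)*xd* = 0.667*xd*. The documents give no value for *x*.
- *d* = 1, *x* = 0.25: 0.167/0.172 = 0.97, rejection about 16% (simulated about 17%); pooled test about 5% to 6%.
- *d* = 1, *x* = 0.50: 0.334/0.172 = 1.94, rejection about 49% (simulated 47% to 49%); pooled test about 9% to 10%.

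**The case against.** Several objections have force.

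- **The pooled test answers a legitimate question.** If plasma shifts a marker and lowers admission, the two are associated in the pooled trial population, and rejecting is correct for that marginal association. This stands. The result is false only if read as a link beyond the arm comparison. But 8.3.4 does not say which question it asks, and the arm comparison of admission is already the primary analysis.
- **The analysis is labelled primarily descriptive.** This stands and limits the consequence: no primary, secondary or stopping decision uses these tests. The same section still attaches a significance threshold to them.
- **Mantel-Haenszel can be stratified.** The strata are not named, so for categorical markers the plan is unspecified, although calling the test univariate points to none. For continuous markers, the t-test or its non-parametric version carries no strata.
- **The sizes need full enrolment and complete samples.** This stands. Collection is only where possible, and if the trial stopped at 51 per arm the pooled rates would be about 6% at 0.5 SD and 10% at 1 SD.
- **Adding an arm term can do harm.** This is the strongest objection, and step 4 confirms it for samples taken after Control-arm plasma. It rules out arm adjustment for every marker and time point, but not for samples taken before admission.

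**Conclusion.** The point holds as a minor improvement to an exploratory analysis. For patient markers sampled after randomization in both arms, the pooled tests in 8.3.4 may report an association that only reflects the arm difference in admission, or may miss a within-arm link. At 8% and 18%, 153 per arm and complete sampling, the false-link rate is about 8% to 10% at a 0.5 SD shift and about 20% at 1 SD; power for a true 0.5 SD link falls from about 82% to about 60% and 31%.

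These figures rest on an assumed shift and on no Control plasma before sampling. They also count all admissions at the 21-day rates of 8.1, whereas 8.3.1 sets the endpoint at 10 days. A test confined to admissions after a day +3 or +7 sample would have fewer events and, at the same rate ratio, smaller effects.

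A reader might infer more than the documents support:
- That a shifted marker will be declared linked. Even at 1 SD, about 80% of trials would not reach significance.
- That every exploratory marker is affected. Plasma-product and pre-infusion measures come from the Treatment arm only and lie outside the mechanism.
- That the primary result is at risk. It does not use these tests.
- That an arm term repairs all time points. Section 5.2.2 allows plasma for admitted Control patients, so it does not.

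**What to change.** In section 8.3.4, for markers sampled in both arms after randomization:

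1. Restrict formal tests to samples taken before admission (for example the day +3 and day +7 swabs), and test the marker against subsequent hospitalization. Use Mantel-Haenszel with randomized arm as stratum for categorical markers. For continuous markers, use logistic regression on marker plus arm, or a van Elteren test stratified by arm. Report within-arm summaries alongside.
2. Keep samples taken after admission out of these tests, including most +2 and +4 week cytokine samples in admitted patients. Describe them by arm, admission status and whether Control-arm plasma had already been given.
3. Keep plasma-product and pre-infusion markers as analyses within the Treatment arm.

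This takes a few sentences and the dates of sampling, admission and any Control-arm plasma. It needs no new patients or visits. The statistical cost is one degree of freedom for arm and fewer samples in the formal tests. The text should be settled before marker data are examined.

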8.4 Charlson Co-morbidity Index22

Patients will be stratified in 4 groups based on their Charlson Co-morbidity Index scoring:

Low score ≤ 3 points; moderate score = 4, 5 points; high score = 6, 7 points; very high score ≥ 8 points.

One Point for each:

- Myocardial infarction (history, not ECG changes only)
- Congestive heart failure
- Peripheral disease (includes aortic aneurysm ≥ 6 cm)
- Cerebrovascular disease: CVA with mild or no residua or TIA
- Dementia
- Chronic pulmonary disease
- Connective tissue disease
- Peptic ulcer disease
- Mild liver disease (without portal hypertension, includes chronic hepatitis)
- Diabetes without end-organ damage (excludes diet-controlled alone)

Two Points for each:

- Hemiplegia
- Moderate or severe renal disease
- Diabetes with end-organ damage (retinopathy, neuropathy, nephropathy, or brittle diabetes)
- Tumor without metastasis (exclude if ≥ 5 y from diagnosis)
- Leukemia (acute or chronic)
- Lymphoma

Three Points for each:

- Moderate or severe liver disease

Six Points for each:

- Metastatic solid tumor
- AIDS (not just HIV positive)

<https://www.mdcalc.com/charlson-comorbidity-index-cci>

9. Regulatory consideration

9.1 Good Clinical Practice

The study will be conducted according to the International Conference on Harmonization (ICH), Good Clinical Practice (GCP), the Declaration of Helsinki, Institutional Review Boards (IRB) and in accordance with the U.S. Code of Federal Regulations on Protection of Human Rights (21 CFR 50).

9.2 Institutional Review Board (IRB) Review

- The final study protocol and consent form (and any other appropriate documents as applicable) will be approved by the Institutional Review Board (IRB) at Hackensack Meridian Health. Approval will be received in writing before initiation of the study.
- Any changes to the study design will be formally documented in protocol amendments and will be approved by the IRB prior to implementation.
- Any amendment to this protocol must also be approved by the IRB and FDA. The written signed approval from the IRB should specifically reference the investigator name, protocol number, study title and amendment number(s) that is applicable. Amendments that are administrative in nature do not require IRB approval but will be submitted to the IRB for information purposes.
- The investigator must keep a record of all communication with the IRB and, if applicable, between a Coordinating investigator and the IRB. This statement also applies to any communication between the investigator (or Coordinating investigator, if applicable) and regulatory authorities.
- Any advertisements used to recruit subjects for the study must be reviewed by [sponsor] and the IRB prior to use.

9.3 Ongoing Information for IRB Committee

As required by legislation and local regulatory requirements, the investigator must submit to the IRB:

- Information on serious or unexpected adverse events as soon as possible
- Annual reports on the progress of the study
- Deviations from the protocol or anything that may involve added risk to subjects

9.4 Investigator Responsibilities

- Investigator responsibilities are set out in the ICH Guideline for Good Clinical Practice and in the local regulations.
- The investigator should ensure that all persons assisting with the study are adequately informed about the protocol, amendments, study treatments, as well as study-related duties and functions.
- The investigator should maintain a list of Sub-Investigators and other appropriately qualified persons to whom he or she has delegated significant study-related duties. The investigator is responsible for keeping a record of all subjects who sign an informed consent document and are screened for entry into the study. Subjects who fail screening must have the reason(s) recorded in the subject's source documents.
- The investigator, or a designated member of the investigator's staff, must be available during monitoring visits to review data, resolve queries and allow direct access to subject records (eg,

medical records, office charts, hospital charts, and study-related charts) for source data verification. The investigator must ensure timely and accurate completion of CRFs and queries.

9.5 Subject information and informed consent

- The investigator must obtain informed consent of a subject and/or a subject's legal representative prior to any study related procedures.
- Documentation that informed consent occurred prior to the study subject's entry into the study and of the informed consent process should be recorded in the study subject's source documents including the date. The original informed consent document signed and dated by the study subject and by the person consenting the study subject prior to the study subject's entry into the study, must be maintained in the investigator's study files and a copy given to the study subject.
- In addition, if a protocol is amended and it impacts on the content of the informed consent, the informed consent document must be revised. Study subjects participating in the study when the amended protocol is implemented must be re-consented with the revised version of the informed consent document. The revised informed consent document signed and dated by the study subject and by the person consenting the study subject must be maintained in the investigator's study files and a copy given to the study subject.

9.6 Confidentiality

- The patient charts, collected data, and all analysis of the data will adhere to HIPAA & institutional patient confidentiality requirements.
- More specifically, a coding system will be used for which a unique identifier (study ID number) will be assigned to each patient name and contact details. Only the study number will be included in the data collection tool, data analysis software and potential publications. The list with the direct identifiers (for the purposes of linking data and keeping track of patients) will be stored separately in a secure server at each site.
- Analytical datasets will be stored on secure servers that also limit access to the investigator team. Should results of the study be published or reported, individual names or other identifying information will not be used.

9.7 Retention of records

Records will be retained in accordance with regulatory, organizational and sponsor requirements, but no less than six (6) years following the completion of the research. Disposal of records will be done in such a manner that no identifying information can be linked to research data.

10. Data handling and recordkeeping

10.1 Data/documents

The investigator must ensure that the records and documents pertaining to the conduct of the study and the distribution of the investigational product are complete, accurate, filed and retained.

The primary source documents for this study will be the subjects' medical records. If the investigators maintain separate research records, both the medical record and the research records will be considered the source documents for the purposes of auditing the study. The investigator will retain a copy of source documents. The investigator will permit monitoring and auditing of these data, and will allow the sponsor, IRB and regulatory authorities access to the original source documents. The investigator is responsible for ensuring that the data collected are complete, accurate, and recorded in a timely manner. Source documentation (the point of initial recording of information) should support the data collected and entered into the study database/case report form and must be signed and dated by the person recording and/or reviewing the data. All data submitted should be reviewed by the site investigator and signed as required with written or electronic signature, as appropriate. Data entered into the study database will be collected directly from subjects during study visits or will be abstracted from subjects' medical records. The subjects' medical records must record their participation in the clinical trial and what medications (with doses and frequency) or other medical interventions or treatments were administered, as well as any AEs experienced during the trial.

10.2 Data management

Study data will be collected at the study site(s) and entered into the study database. Data entry is to be completed on an ongoing basis during the study. Clinical data will be entered into an electronic case report form. The data system includes password protection and internal quality checks to identify data that appear inconsistent, incomplete, or inaccurate.

APPENDIX A

COVID-19 Convalescent Plasma Procurement SOP BMT 800 01

- BMT 800 01, appendices A-L
- BMT 800 01, referenced SOPs

